***Exploratory endpoints:***

Associations between the change in mitochondrial priming at baseline as compared to at the time of duvelisib monotherapy and between baseline and combination therapy and ORR will be assessed using Wilcoxon rank test. Associations between change in the percentage of cytochrome c release in response to the Bad, HRK and MS-1 peptides and ORR will be assessed using the Wilcoxon rank test. We will determine whether the percentage of regulatory T-cells, NK cells or monocytes at the start of therapy, after one week of duvelisib monotherapy, and after three months of combination therapy correlates with ORR, CR rate or toxicity using the Wilcoxon rank test.

The average change in lymph node diameter measured on day 1 and day 8 will be measured on physical exam and recorded in the medical record.

CONFIDENTIAL

This document is confidential. Do not disclose or use except as authorized.

We will also measure the change in total score using the quality of life (QoL) questionnaire in appendix F.

### **13.4 Reporting and Exclusions**

Participants who never start combination therapy will be excluded from analysis in both the phase I and phase II study

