**5.1.2.2 Phase II:**

Patients in the phase II portion of the trial will also begin duvelisib on day 1 and add venetoclax on day 8. Please refer to section 5.1.2 for full venetoclax dose ramp up instructions. Patients will continue combination therapy for up to 12 cycles followed by venetoclax monotherapy until unacceptable toxicity, patient withdrawal, disease progression without clinical benefit, physician decision, physician/patient discussion of treatment discontinuation based on objective disease response, or death. Those patients who achieve CR/CRi with undetectable MRD in the bone marrow after 1 year of combination therapy have the option to discontinue study therapy and be monitored with the option to resume venetoclax monotherapy if at least 2 peripheral blood MRD tests come back as detectable. If they do not achieve MRD negativity or have evidence of disease progression after reaching full dose venetoclax monotherapy, they have the option to add duvelisib at the highest dose they previously tolerated and continue it until MRD negativity is achieved on two successive peripheral blood MRD assessments or indefinitely depending on tolerability.

Patients in the RS cohort will be treated similarly to those in the phase II CLL/SLL cohort with one week of duvelisib monotherapy prior to adding venetoclax. RS patients will also start with 20 mg of venetoclax with weekly ramp-up to 400 mg similar to the CLL/SLL cohort. However, given the potential for rapidly progressive RS, these RS patients will also have the option to undergo an accelerated venetoclax ramp-up modeled after another study of venetoclax plus chemotherapy that was recently reported ([name] et al., ICML, 2019). In that study, venetoclax was safely ramped up in a daily fashion for RS patients, who were monitored closely in the

CONFIDENTIAL

This document is confidential. Do not disclose or use except as authorized.

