## **11. MEASUREMENT OF EFFECT**

### **11.1 Definitions:**

Evaluable for toxicity: All participants who receive at least one dose of study treatment will be evaluable for toxicity from the time of their first treatment.

Evaluable for DLT: All participants who complete the first cycle of combination therapy will be evaluable for DLT from the time of their first treatment. Any patient who experiences a DLT after receiving at least one dose of combination study treatment will also be considered evaluable for DLT. In the phase I portion of the study, if a patient comes off study due to a reason other than a DLT (e.g. disease progression) prior to the end of the DLT observation period, that patient can be replaced.

Evaluable for objective response: Only those participants who have measurable disease present at baseline, have received at least one cycle of therapy, and have had their disease re-evaluated will be considered evaluable for response. These participants will have their response classified according to the definitions stated below. (Note: Participants who exhibit objective disease progression or die prior to the end of cycle 1 will also be considered evaluable.)

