***Phase II Study (CLL/SLL patients):***

***Treatment Efficacy***

The primary endpoint for the phase II study is the rate of complete response (CR) at 12 months according to 2008 IW-CLL criteria. The CR rate will be obtained for all patients at 12 months and will be reported as a percentage of total patients.

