***Phase II Study (Richter’s Syndrome Cohort):***

In a previous study with a commonly used chemoimmunotherapy regimen for RS, dose-adjusted EPOCH-R, the CR rate was 20%. We base this as the null hypothesis. With the addition of

CONFIDENTIAL

This document is confidential. Do not disclose or use except as authorized.

venetoclax, we hypothesize that the CR rate will be 45% or higher. Twenty patients will be enrolled and if 7 or more patients achieve CR we will regard the treatment efficacious. Conversely, if 6 or fewer patients achieve CR, we will regard the treatment inefficacious. With this design, the probability of concluding the treatment efficacious is 0.87 if the true but unknown response rate is 45% and 0.09 if the true rate is 20%. This decision rule is calculated using the exact binomial method. Table 1 below shows the operating characteristics of this design.

Table 1. Operating Characteristics

	True but Unknown CR Rate					
	20%	25%	30%	35%	40%	45%
Prob( $\geq 7$ CR in 20)	0.09	0.21	0.39	0.58	0.75	0.87

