### 13.2 Sample Size, Accrual Rate and Study Duration

We anticipate approximately 12 CLL/SLL patients will be enrolled in the phase I study, using the traditional 3+3 design as described above.

For the phase II study, a Simon two-stage design will be employed whereby a 10% complete response (CR) rate is considered not promising, a 30% complete response rate is considered promising, and the probabilities of a type I error (falsely accepting a non-promising therapy) and type II error (falsely rejecting a promising therapy) are set at 0.10 and 0.10, respectively. In the first stage of this design, 12 CLL/SLL patients will be accrued. All patients will be followed for up to one year. If at least 2 patients achieve CR then an additional 23 CLL/SLL patients will be accrued to the second stage. If 0 or 1 patients achieve CR the study will be terminated and declared negative. The probability of early stopping based on an optimal Simon’s two stage design is 65%. At the end of the trial, if 6 or more patients respond out of a total of 35 patients, then this combination will be considered worthy of further investigation. This design yields at least a 0.90 probability of a positive result if the true response rate is at least 30% and yields a 0.90 probability of a negative result if the true response rate is 10%.

Of note, all patients in the phase I study will be evaluated for response and can be counted in efficacy evaluations in stage 1 of the phase II portion of the trial. An exploratory analysis will also be performed to estimate the rate of CR with confidence intervals in the 29 patients treated at the venetoclax MTD.

For the Richter’s Syndrome Cohort, we plan to accrue 20 additional patients. Given the poor prognosis and lack of a standard of care for this population, we will not have an early stopping rule for this cohort based on efficacy or toxicity.

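### Section 13.4 drops phase II patients lost in the 7-day duvelisib lead-in, against the denominators in 13.1 and 11.1, and so can only raise the reported CR rate

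*Combined protocol and SAP*

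**What the plan says.** Section 13.4 (Reporting and Exclusions) sets a general exclusion: "Participants who never start combination therapy will be excluded from analysis in both the phase I and phase II study".

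Section 5.1.2.2 creates the group that it removes: "Patients in the phase II portion of the trial will also begin duvelisib on day 1 and add venetoclax on day 8". The same section gives the RS cohort the same one-week lead-in.

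Other sections describe the denominator differently:

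- Section 13.1, Treatment Efficacy (CLL/SLL): "The CR rate will be obtained for all patients at 12 months and will be reported as a percentage of total patients".
- Section 11.1, note to the response-evaluable definition: "Participants who exhibit objective disease progression or die prior to the end of cycle 1 will also be considered evaluable".
- Section 13.1, RS cohort: "Twenty patients will be enrolled and if 7 or more patients achieve CR we will regard the treatment efficacious".
- Section 13.2, CLL/SLL: "In the first stage of this design, 12 CLL/SLL patients will be accrued", with the final rule worded "At the end of the trial, if 6 or more patients respond out of a total of 35 patients".

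Replacement of patients is described only for phase I (Sections 5.3, 11.1 and 13.1). No text says whether Section 13.4 overrides the other statements or the reverse.

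**The concern.** CR rate is the phase II primary endpoint. Section 13.4 defines the analysis set by an event after treatment has begun: reaching the first venetoclax dose. Patients can miss that dose because of progression, death, toxicity or withdrawal, and all of these go with treatment failure. The first response scan is at cycle 4 and the first on-treatment marrow at cycle 7, so a patient who leaves in week one cannot be recorded as a CR. Removing such patients shrinks the denominator and leaves the numerator alone.

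Two analysts following different sections could therefore report different primary results from the same data. RS is where this is most likely to show: the cohort has only 20 patients, the protocol itself cites the potential for rapid progression, and the result will be read against a historical CR rate of 20%.

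**Working it through.** **Inputs.** CLL/SLL (Section 13.2): null 10%, alternative 30%, at least 2 CRs in 12 to continue, 23 more patients, at least 6 CRs in 35 at the end. RS (Section 13.1): null 20%, alternative 45%, at least 7 CRs in 20. Lead-in loss: not given in the documents, so every value below is an assumption.

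**1. The plan's own figures.** For CLL/SLL, P(success) = sum over x = 2 to 12 of P(X1 = x) × P(X2 ≥ max(0, 6 − x)), with X1 ~ Bin(12, p) and X2 ~ Bin(23, p). This gives 0.098 at p = 0.10 and 0.901 at p = 0.30. The probability of early stopping under the null is P(X1 ≤ 1) = 0.659. For RS, P(X ≥ 7) with X ~ Bin(20, p) is 0.087 at 0.20 and 0.870 at 0.45. All agree with the stated figures when 12, 35 and 20 are full denominators.

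**2. Effect on the reported rate.** With k excluded non-CR patients, the reported rate is CRs / (N − k).

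| k excluded (assumed) | RS, 7 CRs | CLL/SLL, 6 CRs |
|---|---|---|
| 0 | 7/20 = 35.0% | 6/35 = 17.1% |
| 1 | 7/19 = 36.8% | 6/34 = 17.6% |
| 2 | 7/18 = 38.9% | 6/33 = 18.2% |
| 3 | 7/17 = 41.2% | 6/32 = 18.8% |

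**3. Effect on the decisions without replacement.** Each rule is a count of CRs. Excluded patients contribute no CR, so the count is the same in either set and so is every decision. Type I error judged on all treated patients stays at 0.098 and 0.087. If the null rate is instead defined among combination starters, a 10% loss makes the rate over all treated 0.10 × 0.90 = 0.09 and 0.20 × 0.90 = 0.18. Type I error is then 0.066 (CLL/SLL) and 0.054 (RS), which is lower.

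**4. Effect if excluded patients were replaced.** Suppose 12, 35 and 20 were filled with combination starters, and the true CR rate over all treated patients is at the null. The rate among those analysed is p0 / (1 − f). At f = 10% this is 0.10 / 0.90 = 0.111 and 0.20 / 0.90 = 0.222. Type I error becomes 0.141 (CLL/SLL) and 0.136 (RS).

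**5. Power when all treated patients are counted.** If 30% and 45% are the CR rates among starters and 10% are lost, the rates over all treated are 0.30 × 0.90 = 0.27 and 0.45 × 0.90 = 0.405. Power is then 0.846 (CLL/SLL) and 0.764 (RS). By step 3, these values are the same under Section 13.4 without replacement.

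**The case against.** The best defence is that Section 13.4 is explicit, prespecified and placed under a heading about exclusions. On an ordinary reading a specific exclusion qualifies a general phrase, so total patients in Section 13.1 could mean the total analysed. Enrolled and accrued are recruitment words and need not name an analysis set. The phase II objective concerns the two drugs in combination, which the combination-started set matches, and Section 13.4.1 and the toxicity boundary text also use combination starters.

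Much of this narrows the point. The clash with the Section 11.1 note covers only progression or death in the first seven days; other lead-in stoppers fall outside that note as well. The total-patients sentence stands only under the CLL/SLL heading, so the opposition for RS is thinner. The shift per patient is modest: 0.5 percentage points in CLL/SLL and 1.8 in RS for the first exclusion.

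The defence does not remove the point. Even if Section 13.4 is taken to govern, it still discards treated non-responders from the primary endpoint, and a patient who dies on day 5 is both evaluable (11.1) and excluded (13.4).

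A reader might go further and infer that the go/no-go rules lose their error control. The documents do not support that. The rules are CR counts and no phase II replacement is provided, so the choice of set changes none of the decisions. Nor does counting all treated patients cost power against the plan as written; the drops to 0.846 and 0.764 arise only against a plan that replaces lead-in losses.

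**Conclusion.** The point holds as a bias in the reported primary estimate and a contradiction between sections. It is not a failure of the decision rules. Following Section 13.4 can only raise the reported CR rate: with one to three exclusions, by 1.8 to 6.2 percentage points in RS at 7 CRs and by 0.5 to 1.6 points in CLL/SLL at 6 CRs. The direction is certain; the size is not, because the documents give no lead-in loss.

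Type I error of 0.098 and 0.087 is unaffected provided that nobody in phase II is replaced and the null rate is read as applying to all treated patients. The plan does not expressly rule out replacement in phase II, and at an assumed 10% loss it would bring type I error to 0.141 and 0.136. Section 13.2 also lets phase I patients count in stage 1; these calculations take the 12 as a fixed set of treated patients. The point should be fixed before the CR analysis, so that the denominator is not chosen with results in hand.

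**What to change.** Amend Section 13.4 and align Sections 11.1, 13.1 and 13.2 with it:

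1. The primary phase II CR analysis in both cohorts counts every patient who received at least one dose of either study drug. Patients with no response assessment count as non-CR.
2. The 2/12, 6/35 and 7/20 rules apply to that set.
3. Phase II patients are not replaced.
4. The combination-started set, which matches the objective's wording, is reported as a sensitivity analysis.

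The cost is wording only, with no new data. The reported CR rate may be slightly lower. There is no power loss against the plan without replacement. Against a plan that filled 12, 35 and 20 with combination starters, with the CR rate defined among starters, a 10% loss would lower power from 0.901 to 0.846 (CLL/SLL) and from 0.870 to 0.764 (RS).

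Minor side points: Sections 11.1 and 13.4.1 define evaluable for toxicity differently (any study treatment against combination therapy) and should share one definition for general safety reporting. Section 5.3 describes the DLT window in two ways, which the sponsor should reconcile.

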#### **13.4.1 Evaluation of Toxicity**

All participants who receive at least one dose of combination therapy (duvelisib and venetoclax) will be evaluable for toxicity from the time of their first treatment.

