### 5.3 Definition of Dose-Limiting Toxicity (DLT)

Dose-limiting toxicity (DLT) is based on the CTEP Active Version of the NCI Common Terminology Criteria for Adverse Events (CTCAE) Version 5.0. DLT refers to toxicities experienced at any time during the first cycle of study treatment, defined as the following:

- Grade 4 neutropenia lasting more than 5 days
- Febrile neutropenia of any duration ( $ANC < 1.0 \times 10^9/L$  and fever  $\geq 38.5^\circ F$ )
- Grade  $\geq 3$  thrombocytopenia with clinically significant bleeding
- Grade  $\geq 4$  infection by NCI-CTCAE criteria
- Any grade 3 or greater non-hematologic toxicity with the following exceptions:
  - Grade 3 or greater nausea/vomiting/diarrhea that persists for 7 days or less
  - Grade 3 asymptomatic laboratory abnormalities that improve to grade 2 or less within 3 days
- Any grade  $\geq 3$  diarrhea or vomiting or diarrhea that requires tube feeding, total parenteral nutrition, or requires or prolongs hospitalization
- Inability to receive Day 1 therapy of Cycle 2 after a delay in treatment of up to 21 days due to continued drug related toxicity from the prior cycle
- Severe cutaneous reaction (grade 3 or greater)
- Grade 4 elevation in ALT and/or AST or grade  $\geq 3$  elevation in ALT and/or AST occurring in the context of a Grade  $\geq 2$  elevation in bilirubin
- Grade 5 treatment-related adverse events

All toxicities will be considered relevant to determining DLTs and to reporting unless the event can clearly be determined to be unrelated to the study drug(s).

The DLT observation period is considered the period from the first dose of combination therapy through the completion of cycle 1. In the phase I study, if a patient comes off study due to a reason other than a DLT (e.g. disease progression) prior to the end of the DLT observation period, that patient can be replaced.

CONFIDENTIAL

This document is confidential. Do not disclose or use except as authorized.

Management and dose modifications associated with the above adverse events are outlined in Section 6.

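### Sections 13.4 and 13.4.1 leave out of the toxicity analysis any patient who stops during the duvelisib lead-in, whereas 11.1 includes that patient; the DLT window and the Table 11 denominator also need reconciling

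*Combined protocol and SAP*

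**What the plan says.** **Who is in the toxicity set.** Section 11.1: "All participants who receive at least one dose of study treatment will be evaluable for toxicity from the time of their first treatment". Section 13.4.1 sets a narrower entry condition: "All participants who receive at least one dose of combination therapy (duvelisib and venetoclax) will be evaluable for toxicity". Section 13.4 goes further: "Participants who never start combination therapy will be excluded from analysis in both the phase I and phase II study". No section says which of these takes precedence.

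**From when toxicity is counted.** Sections 11.1 and 13.4.1 agree here. The 13.4.1 sentence ends by saying that patients in its set "will be evaluable for toxicity from the time of their first treatment".

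**The DLT window.** Section 5.3 opens with: "DLT refers to toxicities experienced at any time during the first cycle of study treatment". Later in the same section: "The DLT observation period is considered the period from the first dose of combination therapy through the completion of cycle 1". Section 13.1 uses the first cycle of combination treatment, both for the 3+3 escalation and for the phase II toxicity rule. Section 11.1 is mixed: "All participants who complete the first cycle of combination therapy will be evaluable for DLT from the time of their first treatment". Its second route to DLT evaluability requires the DLT to follow a combination dose.

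**The phase II stopping-rule denominator.** In section 13.1 the text of the rule counts patients with at least one combination dose. The heading of Table 11 counts patients evaluable for toxicity, the term that 11.1 and 13.4.1 define differently.

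**The lead-in.** Footnote 1 of the study calendar has duvelisib given alone on days 1-7 of cycle 1, with the venetoclax ramp-up starting on day 8.

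**The concern.** The lead-in is part of the regimen that every participant receives. Someone who has a severe reaction to duvelisib on day 4 and stops never takes venetoclax. Under 11.1 that patient and that event are in the toxicity analysis; under 13.4 and 13.4.1 neither is. The patient is left out because of the toxicity, so the exclusion depends on the outcome being measured.

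The DLT passages raise a related problem. A qualifying event on day 5 is a DLT under the opening sentence of 5.3 and falls outside the observation period in the later sentence and in 13.1. These definitions feed two decision rules, the 3+3 escalation and the phase II accrual halt. Two analysts working from the same data could apply either rule differently and each cite the protocol.

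**Working it through.** **1. The stated figures, reproduced.** Input: the Table 11 boundaries for n = 1 to 35. Method: exact sequential binomial recursion, stopping when the number of toxicities reaches the boundary.

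| Toxicity rate | 0.10 | 0.20 | 0.30 | 0.40 | 0.50 | 0.60 |
|---|---|---|---|---|---|---|
| Table 12 | 0.048 | 0.436 | 0.865 | 0.988 | 0.999 | 1.00 |
| Recomputed | 0.049 | 0.438 | 0.866 | 0.988 | 1.000 | 1.000 |

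The 3+3 escalation probability is (1-p)^3 + 3p(1-p)^2 × (1-p)^3. At p = 10%, 20% and 30% it gives 0.906, 0.709 and 0.494, against 0.91, 0.71 and 0.49 in section 13.1. Both tables are correct for a given rate. The open question is which patients and events make up that rate.

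**2. Who is affected under each section.**

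| Patient | 11.1 | 13.4 / 13.4.1 |
|---|---|---|
| Toxicity on days 1-7, then starts venetoclax | counted, from first treatment | counted, from first treatment |
| Toxicity on days 1-7, never starts venetoclax | counted | excluded |

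The two definitions part only in the second row.

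**3. Direction.** Excluding one patient who had an event turns k/n into (k-1)/(n-1), which is never larger than k/n. For example, 7/35 = 20.0% becomes 6/34 = 17.6%.

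**4. How many patients.** The documents give no rate of stopping in the lead-in. With an assumed 2%, 5% or 10%, the expected number among 35 is 35 × 0.02 = 0.7, 35 × 0.05 = 1.75 or 35 × 0.10 = 3.5.

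**5. The DLT window and the decision rules.** Let c be the DLT rate in the combination window and l an assumed lead-in DLT rate, independent of c. If lead-in events count, the rate is 1 - (1-l)(1-c); if they do not, it is c. At c = 20%, l = 2% gives 1 - 0.98 × 0.80 = 0.216, l = 5% gives 0.240 and l = 10% gives 0.280. All stopping figures take 35 patients in the denominator.

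| Assumed l | P(stop), c = 10% | P(stop), c = 20% | P(escalate), c = 20% |
|---|---|---|---|
| Lead-in not counted | 0.049 | 0.44 | 0.71 |
| 2%, counted | 0.087 | 0.52 | 0.67 |
| 5%, counted | 0.17 | 0.64 | 0.62 |
| 10%, counted | 0.39 | 0.81 | 0.54 |

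**The case against.** **The DLT window is mostly settled.** Where the documents define the observation period as such, in the later 5.3 sentence and in 13.1, they tie it to combination treatment, and the phase II rule does the same. The outlier is the opening sentence of 5.3. A combination window can also be defended: the MTD sought is that of venetoclax, and duvelisib is 25 mg BID at every level of Table 1, so lead-in events say little about the venetoclax level. This stands. It is why the request on the window is to reconcile the passages, with no claim that the window must start on day 1.

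**Lead-in events are still recorded.** Section 7.5.1 requires SAE reports from consent, section 7.7 puts all adverse events on case report forms, and section 17.9 has everyone receiving investigational agents evaluated for safety. This also stands. The gap is in the analysis set, not in data collection.

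**Stronger readings that the documents do not support.**

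- A reader might infer that 13.4.1 discards all lead-in toxicity. It does not: its clock starts at first treatment, so only patients who never take venetoclax are lost.
- A reader might infer a fall in stopping probability from 0.87 to 0.72 at a true 30% rate. That takes DLTs as evenly spread over a 49-day cycle 1, so that 0.30 × 6/7 = 0.257 is counted. Nothing in the documents supports even spread, and section 5.4.1 places the highest tumor lysis risk at venetoclax initiation, after the lead-in. The figure also keeps the lead-in cases in the denominator as event-free. If they leave it, the rate is 0.257/(1 - 0.30/7) = 0.269 and the recursion gives about 0.77.
- A reader might infer that a 28-day cycle 1 under the accelerated ramp-up loses a quarter of the monitored window. That option is for Richter's patients, for whom 13.2 sets no toxicity stopping rule, and the documents do not state a 28-day cycle 1 for it.

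**Conclusion.** The contradiction between 11.1 and 13.4/13.4.1 is real and stands in the current text. It is confined to patients who stop before day 8. For those who stop because of toxicity, the exclusion can only lower the reported toxicity. The DLT sentences in 5.3 and the two denominators for Table 11 are a separate inconsistency that bears on escalation and on the accrual halt.

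The size cannot be fixed from the documents. Under assumed lead-in rates of 2% to 10%, it ranges from under one patient in 35 to three or four. At a 20% combination-window rate, counting lead-in DLTs moves the stopping probability from 0.44 to between 0.52 and 0.81. These figures rest on the assumed rates, on independence of lead-in and combination-window events, and on 35 patients in the denominator. Tables 11 and 12 contain no arithmetic error.

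**What to change.** 1. In 13.4.1, change the entry condition from a dose of combination therapy to a dose of study treatment, as in 11.1.
2. In 13.4, state that the exclusion of patients who never start the combination does not apply to the toxicity analysis.
3. Reconcile the two 5.3 sentences, 11.1 and 13.1 to one DLT window. Which window is a dose-finding decision for the sponsor.
4. Use one denominator in the text of the phase II rule and in the heading of Table 11, consistent with that window.
5. Whichever window is kept, report days 1-7 toxicity for everyone who took duvelisib, including those who stopped before venetoclax.

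Items 1, 2 and 5 cost wording and a slightly larger denominator. No new data are needed, since the study calendar already has adverse event evaluation on day 1 and day 8, and reported toxicity may rise a little. Items 3 and 4 need more thought: moving the window to day 1 would change which events drive escalation and the accrual halt, whereas keeping the combination window needs only a correction to the opening 5.3 sentence and agreement of the 11.1 clock with it.
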